4.5. Benefit-Risk Analysis

Galidesivir is a parenterally available small molecule nucleoside analog inhibitor of viral RNA polymerase activity, mediated through non-obligate RNA chain termination. Nucleoside analogs

have a proven mode of action in the treatment of multiple human viral infections. As a class, some nucleoside analogs have been associated with serious adverse reactions, including peripheral neuropathy, myopathy, pancreatitis, and lactic acidosis with hepatic steatosis, resulting from mitochondrial toxicity following chronic dosing (Lund, Peterson et al. 2007). There is no evidence in the literature of acute severe adverse reactions resulting from treatment with nucleoside analogs following single doses or up to 1 week of dosing.

- Toxicity studies in the cynomolgus monkey and rat have been conducted with IV infusion administration. Although C_{max} and AUC are lower following IV infusion compared with IM injection, no new findings have been identified from IV infusion toxicology studies. Therefore, the IM studies provide useful toxicological information to develop appropriate monitoring in an IV study.
- Toxicology studies in rats and monkeys summarized in the IB suggest that the primary target organs of galidesivir toxicity following IM administration in the rat were the kidney and liver, with toxicities also observed in the spleen, testes, thymus, heart, hematopoietic system, and injection sites. Target organs of systemic toxicity in the monkey were kidney, liver, lymphoid system, and injection sites. The principal target organ of systemic toxicity in rats and monkeys following IV infusion was the kidneys (Section 4.2.3). Microscopic changes in liver and kidney correlated to monitorable changes in relevant clinical chemistry analytes and were reversible. The large intestine was also a target in rats at the highest dose examined; minimal-to-mild single cell necrosis/degeneration in the cecum (with colon and rectum less frequently affected), with or without concurrent mucosa crypt epithelium hyperplasia/hypertrophy and/or mucosa inflammation. Galidesivir is compatible with human blood and does not cause hemolysis at concentration up to and including 15 mg/mL.

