8.2. Subject Exclusion Criteria

Subjects must not meet any of the following exclusion criteria to be eligible for participation in this study:

- 1. Any clinically significant medical conditions or medical history that, in the opinion of the Investigator or Sponsor, would interfere with the subject's ability to participate in the study or increase the risk of participation for that subject*.

*Note: Significant medical history would include, but not be limited to, kidney disease with creatinine clearance $<$ 90 mL/min/1.73m², known active liver disease (including steatosis), ischemic heart disease, cardiac conduction disorder, chronic intestinal disease, hypertension (including treated), arrhythmia requiring treatment, diabetes requiring insulin, neuropathy, myopathy, and malignancy (not including squamous cell skin cancer, basal cell skin cancer, or cervical low-grade squamous intraepithelial lesions).

2. Any clinically significant psychiatric condition or history of psychiatric condition that, in the opinion of the Investigator or Sponsor, would interfere with the subject's ability to participate in the study or increase the risk of participation for that subject.
3. Abnormal ECG at the screening visit*.

*Note: Abnormalities include, but are not limited to, a QTcF > 450 ms in men or > 460 ms in women, a PR > 220 ms, or ventricular and/or atrial premature contractions that are more frequent than occasional, and/or as couplets or higher in grouping, second or third degree heart block, or long QT syndrome.

4. Clinically significant abnormalities found on the screening echocardiogram*.

*Note: Abnormalities include but are not limited to: ejection fraction (EF) <55% or structural abnormality including valvular and septal defects. Incident mitral valve prolapse (MVP) with none-to-trace regurgitation is not an exclusion.

5. Known family history of sudden death or long QT syndrome, or family or personal history of QT prolongation, or poison/drug induced arrhythmia that required medical intervention.
6. History of or current implanted defibrillator or pacemaker.
7. Any inclusion laboratory test performed at screening with an abnormal result that is DMID Grade 1 or greater. The inclusion tests are defined to be: alanine aminotransferase (ALT), aspartate aminotransferase (AST), total bilirubin, creatinine, urine protein, hemoglobin, serum potassium, and white blood cell count ([Table 6](#)).

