Laboratory abnormalities outside of the normal laboratory reference ranges and associated grades (according to study specific DMID criteria (modified 2014 DMID Adult Toxicity Grading Scale) see APPENDIX A) should be denoted where possible. For those analyte results that are out of the normal range and do not have an established DMID toxicity criteria, the PI should assess the abnormalities and provide severity grading as defined in Section 11.4.1.2.

All laboratory samples will be analyzed by a local laboratory associated with the site. Reference ranges for each local laboratory will be provided to the Sponsor and included in data listings. For

out-of-range laboratory findings, the interpretation of clinically significant or not clinically significant should be denoted in the source records. Clinically significant laboratory findings in the opinion of the Investigator should be recorded as AEs and handled as described in Section 11.4. Laboratory abnormalities that are not deemed to be clinically significant by the Investigator are not reported as AEs. All laboratory findings will be summarized and reported with appropriate grading, regardless of whether or not they are reported as AEs.

Cystatin C, NGAL, testosterone, CK-MB, troponin and UACR will be analyzed as outlined in the Statistical Analysis Plan. Briefly, changes from baseline will be measured for each analyte. Values outside the normal limits, if applicable, will be graded based on fold changes in comparison to the upper or lower limit of normal. Marked changes in these analytes will be taken as potential indications of impaired organ function and qualitative interpretation will take into account subject incidence, clinical course, and comparison to placebo for the safety analyses in the final study report.

Table 8: Clinical Safety Laboratory Evaluations

Chemistry	Hematology
Albumin Alkaline phosphatase (ALP) [#] Alanine aminotransferase (ALT) [#] Aspartate aminotransferase (AST) [#] Bilirubin (total and direct) [#] Blood glucose Blood urea nitrogen (BUN) Electrolytes (calcium, sodium, potassium, chloride*, phosphorous) Creatine Phosphokinase Creatinine and calculated creatinine clearance [#] Total serum protein Amylase with reflex lipase	Hemoglobin [#] Hematocrit* Erythrocytes* White blood cell count [#] , White blood cell count differential (lymphocytes, monocytes*, neutrophils, eosinophils, and basophils*) Platelets
Urinalysis	Additional Laboratory Tests

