11.5.2. Dose Escalation Committee

Following the completion of each cohort, the DEC will meet to decide if the required safety parameters have been met. All available safety data for all subjects in a given cohort through 96 hours and PK data through 24 hours post-dose will be reviewed by the Sponsor Medical Monitor, Clinical Pharmacologist, and PI and used in the decision to escalate to the next higher dose. Review meetings will be held following each dose level of Cohorts 1 to 4.

An interim Safety Summary Report will be prepared for review by the DEC that will document the following safety findings for each dose cohort:

- Demographics
- Dosing information, including any subjects who discontinued dosing
- Listing of any SAEs with assessment of severity
- Listing of AEs with assessment of severity
- Listing of any graded clinical chemistry findings

- Listing of all clinical chemistry findings Grade 2 or higher
- Listing of any graded hematology findings
- Listing of all hematology findings
- Listing of any graded urinalysis findings
- Listing of all urinalysis findings
- Listing of vital signs
- Listing of QT findings
- Telemetry findings
- Additional narrative summaries
- Listing of subjects who terminated early
- Listing of PE data

An interim PK report will be prepared for review by the DEC that will document the following PK findings for each dose cohort:

- Preliminary plasma PK parameters (through 24-hours post-dose) based upon nominal times: AUC; C_{max} , T_{max} , terminal elimination half-life ($t_{1/2}$; median, minimum, maximum, geometric mean, coefficient of variation [CV%])
- Predictions of C_{max} and AUC values for the next cohort, where relevant

The interim Safety Summary and PK report documents will form the basis of teleconferences involving the Sponsor and the PI to evaluate each completed cohort in the study. The DEC will use the Dose Escalation Criteria to determine whether escalation as planned per protocol may commence.

Dose Escalation Criteria

The study will proceed to the next planned dose level if **NONE** of the following is met:

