12.3.1.3. Analysis of Safety Variables

AEs will be mapped to a Medical Dictionary for Regulatory Activities (MedDRA) preferred term (PT) and system organ classification (SOC). Any event reported on the subject's study record that occurs on or after the initiation of study drug is defined as treatment emergent. Additionally, it is assumed that an AE that is reported to have started on Day 1 of a given treatment period without an associated onset time may have occurred after the initiation of study drug. Hence, AEs occurring on Day 1 with no associated onset time will be assumed to be treatment emergent. The occurrence of TEAEs will be summarized by cohort and treatment assignment using MedDRA PTs, SOCs, and severity. Separate summaries of treatment-emergent SAEs and AEs considered to be related to study drug will be generated. All AEs will be listed for individual subjects showing both verbatim and preferred terms.

Descriptive summaries of vital signs, ECG parameters (12 lead and telemetry), ECHOs, and clinical laboratory results will be presented separately for each cohort by study visit and treatment assignment. Laboratory abnormalities will be graded according to the modified DMID criteria ([APPENDIX A](#)).

Any graded abnormality that occurs following the initiation of study drug and represents at least one grade increase from the baseline assessment is defined as treatment emergent. The number and percentage of subjects experiencing treatment-emergent graded toxicities will be summarized by treatment group. Laboratory toxicity shifts from baseline to post-baseline assessments will be summarized by treatment group.

PE results will be presented in listings. Changes in PE results that are AEs will be reported in AE tables.

Concomitant medications will be coded using the World Health Organization (WHO) Dictionary. These data will be summarized by cohort and treatment assignment.

Subjects receiving placebo will be pooled and reported together across cohorts.

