### 17.1.3 Laboratory Data

Clinical laboratory data will be presented using units from the study data tabulation model (SDTM) Controlled Terminology.

A descriptive statistics summary of continuous laboratory results and derived changes from baseline for cardiac markers, chemistry, coagulation, hematology, and urinalysis will be provided by cohort and scheduled timepoint.

Laboratory abnormalities outside of the normal laboratory reference ranges and associated grades (according to study specific DMID criteria specified in the 2014 DMID Adult Toxicity Grading Scale in Appendix 5) should be denoted where possible. For those analyte results that are out of the normal range and do not have an established DMID toxicity criteria, the severity grading will be provided by the PI. The number and percentage of subjects experiencing treatment-emergent graded toxicities will be summarized.

A shift table describing the change in continuous clinical laboratory values from baseline to follow-up (number and percentage of subjects) will also be provided. The following categories will be used: Normal, DMID Grade 1, DMID Grade 2, DMID Grade 3, DMID Grade 4.

All laboratory data will be listed by subject, including laboratory variables not listed in the protocol.

A separate listing of out-of-range values will also be provided. Normal ranges will be used directly from the clinical laboratory and will be included in the listings for reference. Flags for high and low values will be provided in the listings.

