All Other conditions	Mild (Grade 1)	Moderate (Grade 2)	Severe (Grade 3)
Illness or clinical adverse event (as defined according to applicable regulations)	Transient or mild symptoms; no limitation in activity; no intervention required. The AE does not interfere with the participant's normal functioning level. It may be an annoyance.	Symptom results in mild to moderate limitation in activity; no or minimal intervention required. The AE produces some impairment of functioning, but it is not hazardous to health. It is uncomfortable or an embarrassment.	Symptom results in significant limitation in activity; medical intervention may be required. The AE produces significant impairment of functioning or incapacitation.

Laboratory Adverse Events					
Blood, Serum, or Plasma *	Reference Range **		Mild (Grade 1)	Moderate (Grade 2)	Severe (Grade 3)
Sodium – Hyponatremia mEq/L	135-146 mmol/L		134 – <LLN	132 – 133	<132
Sodium – Hypernatremia mEq/L	135-146 mmol/L		>ULN – 147	148 – 149	>149
Potassium – Hyperkalemia mEq/L	3.5-5.3 mmol/L		>ULN – 5.4	5.5 – 5.6	>5.6
Potassium – Hypokalemia mEq/L	3.5-5.3 mmol/L		<LLN-3.4	<3.4 – 3.3	<3.3
Glucose – Hypoglycemia mg/dL	65-99 mg/dL		62 – 64	52 – 62	<52
Glucose – Hyperglycemia Fasting – mg/dL	65-99 mg/dL		>ULN - 100	101 – 110	>110
Glucose – Hyperglycemia Random – mg/dL	65-139 mg/dL		140 – 159	160 – 200	>200
Blood Urea Nitrogen mg/dL	7-25 mg/dL		26 – 29	30 – 34	>34
Creatinine (Male) – mg/dL	18Y-19Y	0.60-1.26 mg/dL	>ULN – 1.36	>1.36 – 1.56	>1.56
	20Y-49Y	0.60-1.35 mg/dL	>ULN – 1.45	>1.45 – 1.65	>1.65
	50Y-59Y	0.70-1.33 mg/dL	>ULN – 1.43	>1.43 – 1.63	>1.63
Creatinine (Female)- mg/dL	18Y-19Y	0.50-1.00 mg/dL	>ULN – 1.10	>1.10 – 1.30	>1.30
	20Y-49Y	0.50-1.10 mg/dL	>ULN – 1.20	>1.20 – 1.40	>1.40
	50Y-59Y	0.50-1.05 mg/dL	>ULN – 1.15	>1.15 – 1.35	>1.35
Calcium – hypocalcemia mg/dL (Male)	18Y-19Y	8.9-10.4 mg/dL	8.8 – <LLN	8.3 – 8.7	<8.3
	20Y-133Y	8.6-10.3 mg/dL	8.5 – <LLN	8.0 – 8.4	<8.0
Calcium – hypocalcemia mg/dL (Female)	18Y-19Y	8.9-10.4 mg/dL	8.8 – <LLN	8.3 – 8.7	<8.3
	20Y-49Y	8.6-10.2 mg/dL	8.5 – <LLN	8.0 – 8.4	<8.0
	50Y-133Y	8.6-10.4 mg/dL	8.5 – <LLN	8.0 – 8.4	<8.0
Calcium – hypercalcemia mg/dL (Male)	18Y-19Y	8.9-10.4 mg/dL	>ULN – 10.5	10.6 – 11.0	>11.0
	20Y-133Y	8.6-10.3 mg/dL	>ULN – 10.4	10.5 – 10.9	>10.9
Calcium – hypercalcemia mg/dL (Female)	18Y-19Y	8.9-10.4 mg/dL	>ULN – 10.5	10.6 – 10.9	>10.9
	20Y-49Y	8.6-10.2 mg/dL	>ULN – 10.3	10.4 – 10.7	>10.7

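### A within-range creatinine rise of about 1.5-fold can be tabulated as Normal and counted nowhere, although the kidney is the principal nonclinical target organ by the IV route

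*SAP*

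**What the plan says.** Protocol 4.5 (Benefit-Risk Analysis) identifies the organ of interest: "The principal target organ of systemic toxicity in rats and monkeys following IV infusion was the kidneys". Protocol 11.3.1.7, Table 8, collects "Creatinine and calculated creatinine clearance" among the chemistry tests.

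Laboratory toxicity is counted on the modified DMID scale. Protocol 12.3.1.3 defines a treatment-emergent toxicity as "Any graded abnormality that occurs following the initiation of study drug and represents at least one grade increase from the baseline assessment". SAP 17.1.3 tabulates those toxicities and adds a shift table: "The following categories will be used: Normal, DMID Grade 1, DMID Grade 2, DMID Grade 3, DMID Grade 4". The creatinine rows in SAP Appendix 5 (the same as Protocol Appendix A) start Grade 1 just above the ULN. The reference range at ages 20-49 is "0.60-1.35 mg/dL" for men and "0.50-1.10 mg/dL" for women. (Appendix 5 stops at Grade 3, so the Grade 4 category has no definition. That is a separate, minor point.)

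Eligibility keeps screening creatinine at or below the ULN, because Protocol 8.2 excludes "Any inclusion laboratory test performed at screening with an abnormal result that is DMID Grade 1 or greater" and names creatinine among those tests.

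For escalation, Protocol 11.5.2 gives the DEC two chemistry listings: graded findings, and "Listing of all clinical chemistry findings Grade 2 or higher". Hematology and urinalysis each get a listing of graded findings and a listing of all findings.

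**The concern.** Subjects enter with ungraded creatinine, so each has some distance to travel before a rise earns a grade. That distance depends on where the subject starts within the range, not on how much renal function has changed. A subject with a low baseline can lose a sizeable fraction of clearance and remain in the Normal-to-Normal cell. A subject starting at the ULN reaches Grade 3 after a small relative rise.

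At stake is the primary safety objective for the organ that the animal IV data single out. The report could state that no treatment-emergent creatinine toxicity occurred although a subject's clearance had fallen by about a third, and the scheduled chemistry listings used for escalation would not have shown that subject.

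The SAP already handles this kind of problem elsewhere. In 17.1.5, QTcF gets both absolute categories and categories of individual change from baseline. Creatinine gets only the absolute kind.

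**Working it through.** The plan states no figure for this point, so there is none to reproduce. The inputs are the creatinine cut-offs in SAP Appendix 5.

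**Formulas.** LLN is the lower limit of normal.
- Largest rise that stays Normal = ULN / LLN.
- Highest baseline from which an f-fold rise stays Normal = ULN / f.
- Share of range width = (ULN / f − LLN) / (ULN − LLN).

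| Band | Range (mg/dL) | ULN/LLN | 1.5-fold stays Normal up to (share of width) | 1.9-fold stays Normal up to (share of width) |
|---|---|---|---|---|
| Men 18-19 | 0.60-1.26 | 2.10 | 0.84 (36%) | 0.66 (10%) |
| Men 20-49 | 0.60-1.35 | 2.25 | 0.90 (40%) | 0.71 (15%) |
| Men 50-59 | 0.70-1.33 | 1.90 | 0.89 (30%) | 0.70 (0%) |
| Women 18-19 | 0.50-1.00 | 2.00 | 0.67 (33%) | 0.53 (5%) |
| Women 20-49 | 0.50-1.10 | 2.20 | 0.73 (39%) | 0.58 (13%) |
| Women 50-59 | 0.50-1.05 | 2.10 | 0.70 (36%) | 0.55 (10%) |

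Worked example, men 20-49, f = 1.5: 1.35 / 1.5 = 0.90, and (0.90 − 0.60) / (1.35 − 0.60) = 0.40.

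**Size in terms of clearance.** If clearance is inversely proportional to creatinine, the fall is 1 − 1/f. For f = 1.5 that is 33%. A man aged 20-49 going from 0.80 to 1.35 mg/dL has f = 1.69 and a fall of 1 − 0.80/1.35 = 41%, still Normal. A woman aged 20-49 going from 0.70 to 1.10 has f = 1.57 and a fall of 36%, still Normal.

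**Where the scale does register a large rise.** From mid-range at ages 20-49, a 1.9-fold rise gives 0.975 × 1.9 = 1.85 mg/dL (men) and 0.80 × 1.9 = 1.52 mg/dL (women). Both exceed the Grade 3 cut-offs of 1.65 and 1.40. A 1.9-fold rise is Grade 3 from any baseline above 1.65 / 1.9 = 0.87 (men) or 1.40 / 1.9 = 0.74 (women). From the ULN, Grade 3 needs only 1.66 / 1.35 = 1.23-fold or 1.41 / 1.10 = 1.28-fold.

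**How many subjects.** Shares of range width are not shares of subjects, and the documents give no baseline distribution. As an assumption, take normally distributed baselines at ages 20-49: men with mean 0.85 to 1.05 and SD 0.13, women with mean 0.65 to 0.85 and SD 0.10 mg/dL. The share in whom an f-fold rise would stay Normal is Φ((ULN/f − mean)/SD).
- f = 1.5: about 12% to 65% of men and 12% to 80% of women.
- f = 1.9: about 0.5% to 14% of men and 0.3% to 24% of women.

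The ranges are wide because the answer depends strongly on the assumed mean.

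**The case against.** The strongest reply is that the change is neither lost nor hidden.

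- SAP 17.1.3 summarises chemistry change from baseline, 9.1.3 includes the minimum and maximum, and all laboratory data are listed by subject. With six active subjects per cohort, a rise can be traced.
- Creatinine is not the only renal measure. Protocol 4.5 adds NGAL and cystatin C, and Table 8 adds UACR, BUN and urine protein. Protocol 11.3.1.7 commits to change from baseline for cystatin C, NGAL and UACR, with comparison to placebo.
- The investigator or a designee reviews post-dose laboratory results within 12 hours of receipt, and the sponsor sees on-treatment chemistry in real time. A clinically significant change from baseline can be an adverse event (Protocol 11.4.1.1).
- The DEC reviews whatever safety data are available through 96 hours, including narratives.
- Calculated clearance has no DMID row, so an out-of-range value, if the laboratory gives a range, would be graded by the investigator.

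All of this stands, and it limits the point. None of these routes, however, is triggered by a within-range rise, and none counts such rises. The change summary is in absolute units by timepoint, and SAP 9.1.5 generally leaves unscheduled values out of it. High and low flags and the out-of-range listing depend on the normal range. Protocol 11.3.1.7 requires a judgement of clinical significance only for out-of-range results. Cystatin C, NGAL and UACR are sampled after dosing only at discharge and follow-up, are graded by fold of the normal limits, and are not named in SAP 17.1 or 17.1.3.

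Two stronger readings are tempting. A reader might infer that near-doublings in general go uncounted. The cut-offs do not support that: a 1.9-fold rise escapes only from the lowest 0% to 15% of the range width, and from mid-range it is Grade 3. A reader might also infer that the DEC could not learn of such a rise. The gap is in two scheduled listings, not in everything the DEC may see.

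**Conclusion.** The concern holds in a limited form. Creatinine is counted as toxicity only above the ULN, so a rise of about 1.5-fold can be tabulated as Normal from baselines covering 30% to 40% of the range width, depending on band. At ages 20-49 the limits are 0.90 mg/dL (men) and 0.73 mg/dL (women). The corresponding one-third fall in clearance assumes inverse proportionality; the documents give no clearance formula. A near-doubling can be missed only from a low baseline: at or below 0.71 (men) or 0.58 mg/dL (women) at ages 20-49.

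The documents do not support saying that the plan cannot register renal harm, or that kidney toxicity is an established human effect. Protocol 4.5.1 reports that the earlier IM study confirmed none of the nonclinical risks as clinical signals. What is missing is a count and a flag for individual relative change. Adding them is a cheap and worthwhile improvement; nothing here invalidates the analysis.

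**What to change.** In SAP 17.1.3, add one table by dose and pooled placebo giving each subject's maximum post-dose/baseline ratio for serum creatinine and for cystatin C, and the minimum ratio for calculated creatinine clearance. Report descriptive statistics and the number of subjects in ratio categories that the sponsor fixes in advance, in the manner of the QTcF change categories in 17.1.5. State whether unscheduled values count towards the maximum and minimum. Add a by-subject listing of baseline, extreme value and ratio.

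For any DEC review still to come, amend Protocol 11.5.2 so that the interim Safety Summary Report lists all creatinine values with their ratio to baseline. The SAP file already carries completed escalation reports, so this part may have little remaining use; the SAP table is useful either way.

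The grading scale and the escalation and halting criteria are untouched.

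The cost is SAP wording, one table and one listing from data already collected, plus a protocol amendment if the DEC listing is added. Some ratios will reflect ordinary within-subject variation. The placebo column shows this, although with 4 × 2 = 8 planned placebo subjects it does so only roughly.
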